
 To compare the pharmacokinetic concentrations following a single intramuscular dose of CAB LA 600 mg in VT, CT, and CVF relative to blood plasma and CVF in healthy women, and in RT and RF relative to blood plasma and RF in healthy men and women (as data permit). 	
 Concentration ratios including VT: blood plasma, CT: blood plasma, CVF: blood plasma, CT: CVF, VT: CVF in women, and RT: blood plasma, RF: blood plasma and RT: RF in men and women (as data permit) at matched timepoints evaluated.

 To describe the pharmacokinetic profile of CAB LA in blood plasma and CT, CVF, in healthy women and in RT and RF in healthy men and women (as data permit) following a single 600 mg intramuscular dose. 	
 Maximum observed concentration (C_{max}) and time of maximum observed concentration (t_{max}) in blood plasma and in CT, CVF, RT, RF matrices. Area under the concentration time curve from time zero to last quantifiable time point (AUC(0-last)), area under the concentration time curve from time zero to infinity (AUC(0-∞)), area under the concentration time curve from time zero to Week 4 (AUC(0-Wk4)), area under the

Objectives	Endpoints
	concentration time curve from time zero to Week 8 (AUC(0-Wk8)) area under the concentration time curve from time zero to Week 12 (AUC(0-Wk12)) and apparent terminal phase half-life ($t_{1/2}$) in blood plasma, CT, CVF, RT, RF, as data permit. 
 Tissue:blood plasma and fluid:blood plasma ratio of AUCs of intervals specified above.

 To determine the trough concentration achieved following repeat administration of oral CAB 30 mg once daily to steady state in blood plasma and VT, CT, and CVF in healthy women and in RT and RF in healthy men and women (as data permit). 	
 CAB concentration (C_{24}) following oral administration in VT, CT, CVF, RT, RF and blood plasma.

 To assess the safety and tolerability of CAB following repeat oral doses and single dose intramuscular administration in healthy subjects. 	
 Safety and tolerability parameters, including adverse events, clinical laboratory tests, and vital signs assessments.
Exploratory	

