4.4. Design Justification

The rectal and vaginal mucosa are likely relevant sites of CAB action when used to prevent sexual HIV transmission. After IM injection of 400 mg of CAB LA in earlier PK studies, tissue to plasma ratios were low, at 16-28% for cervicovaginal tissue and <8% for colorectal tissue [Spreen, 2014]. The aim of this study is to determine the multi-site PK of CAB LA IM for 12 weeks following a 600 mg IM dose.

Because the current planned CAB LA injection dose frequency is every 8 weeks, we plan PK sampling of blood plasma, cervicovaginal and rectal luminal fluid, and biopsies of cervical, vaginal, and rectal tissue at the end of the 4 week oral lead-in and at 1 week, 4 weeks, 8 weeks, and 12 weeks post-injection to understand drug exposure at all of these

sites throughout a dosing interval and as concentrations wane through Week 12 post-injection. An additional luminal fluid (CVF and/or RF) and tissue (CT/VT and/or RT) sample will be collected on Day 3 (approximately 48 hours post-injection) to assess the early distribution of CAB into the genital tract and rectal compartments. In addition to the paired blood plasma samples, blood plasma will be collected at additional timepoints through the extended safety visits for approximately one year after injection as outlined in Section 7.1. This sampling scheme will provide a comprehensive assessment of CAB LA PK following a single 600 mg IM dose (Table 4).

Table 4 Compartmental PK Sampling

Compartmental PK Sampling Times		
Sex	Oral Lead-In	Post 600 mg IM Dose
Females (BP/VT/CT/CVF/RT ¹ /RF ¹)	Day 29 Rectal fluid and rectal tissue is optional ¹	Day 3 (48h), Day 8 (168h), Week 4, Week 8, Week 12 Rectal fluid and Rectal tissue optional at each timepoint ¹ ; Vaginal tissue will be collected only on Day 3 (48h) and Week 8.
Males (BP/RT/RF)	Day 29	Day 3 (48h), Day 8 (168h), Week 4, Week 8, Week 12

1. Female subjects will be given the choice to provide near simultaneous paired rectal compartment samples at each fluid and tissue sampling time-point. This is an optional assessment for which women must provide consent. Female subjects who do not wish to participate in rectal PK sampling may still participate in the study.
		

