9.2. Sample Size Considerations

9.2.1. Sample Size Assumptions

There was no formal calculation of power or sample size for this study.

Approximately 20 healthy subjects from up to two clinic sites will be enrolled in oral lead-in phase such that approximately 16 evaluable subjects (8 males and 8 females) will receive a CAB IM injection and complete 12 weeks of PK sampling.

Based upon the pharmacokinetic data generated in previous pharmacokinetic tissue studies and the complexity and intensity of sampling of plasma and tissue in this study, the proposed sample size of 16 evaluable subjects (8 women and 8 men) will allow for an informative assessment and description of pharmacokinetic parameters.

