8. PHARMACOKINETIC ANALYSES

The reconciliation of the PK Case Report Form (CRF) and SMS2000 data will be performed by, or under the direct auspices of, Clinical Pharmacology Sciences and Study Operations (CPSSO), GlaxoSmithKline.

The merge of PK concentration data, randomisation and CRF data will be performed by, or under the direct auspices of, Clinical Statistics (Programmer), GlaxoSmithKline.

Derivation of pharmacokinetic parameters will be performed by, or under the direct auspices of, Clinical Pharmacokinetic Modelling Simulation (CPMS), GlaxoSmithKline.

Statistical analysis of pharmacokinetic parameters will be performed by, or under the direct auspices of, Clinical Statistics (Statistician), GlaxoSmithKline.

	Pharmacokinetic Concentration Data					
PC Windows Non- Linear (WNL) File	PC WNL file (CSV format) for the non compartmental analysis by Clinical Pharmacology Modelling and Simulation function will be created according to GSK PK guidance Note: Concentration values will be imputed as per GUI_51487					
Descriptive Summary Statistics, Graphical Displays and Listings	Refer to IDSL PK Display Standards. Refer to IDSL Statistical Principle 6.06.1. Note: Concentration values will be imputed as per GUI_51487 for descriptive summary statistics/analysis and summarized graphical displays only.					
Pharmacokinetic Para	ameter Derivation					
PK Parameter to be Derived by Programmer	The following PK parameters will be derived or extracted from SDTM PC file or SDTM PP by the Programmer: From SDTM PC Concentrations: Ctau on Day 29, C48h, C8d, CWk4, CWk8, CWk12, CWk24, CWk36, and CWk52 from concentration data (as data permit) & the ratios: VT:blood plasma, CT:blood plasma, CVF:blood plasma, CT:CVF, VT:CVF in women, and RT:blood plasma, RF:blood plasma and RT:RF in men and women (as data permit) at matched timepoints evaluated. From SDTM PP file: VT:blood plasma, CT:blood plasma, CVF:blood plasma, CT:CVF, VT:CVF in women, and RT:blood plasma, RF:blood plasma and RT:RF in men and women ratios for Cmax, AUC(0- ∞), AUC(0-last), AUC(0-Wk4), AUC(0-Wk8) and AUC(0-Wk12)					
Pharmacokinetic Para	ameter Data					
Is NQ impacted PK Parameters Rule Being Followed	Yes, refer to Standards for the Transfer and Reporting of PK Data using HARP.					
Descriptive Summary Statistics, Graphical Displays and Listings	Refer to IDSL PK Display Standards & refer to Standards for the Transfer and Reporting of PK Data using HARP.					

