8.1. Reporting Standards for Pharmacokinetic

8.2. Drug Concentration Measures

CAB concentrations will be collected at following time points after a single CAB 600 mg IM dose:

- Blood plasma (BP) of CAB concentrations: Day 1 (pre-dose, 4hr), Day 3 (C48h), Day 5 (C96h), Day 8 (C168h), Weeks 4, 8, 12, 24, 36, and 52 (CWk4, CWk8, CWk12, CWk24, CWk36 and CWk52)
- Cervical tissue (CV) and cervicovaginal fluid (CVF) of CAB concentrations in women: Day 3 (C48h), Day 8 (Cd8), Weeks 4, 8, and 12 (CWk4, CWk8, and CWk12)
- Rectal tissue (RT) and rectal fluid (RF) in men and women (as data permit): Day 3 (C48h), Day 8 (Cd8), Weeks 4, 8, and 12 (CWk4, CWk8, and CWk12)

• Vaginal tissue (VT) of CAB concentrations in women: Day 3 (C48h), and Week 8 (CWk8)

These concentrations will be determined directly from concentration-time data from each matrix (BP, CV, CVF, RT, RF, VT). Descriptive statistics (i.e. mean, standard deviation, median, minimum and maximum) and graphics will be created to describe the primary PK endpoints of interest.

Refer to the standard operating procedure, SOP-CPK-0001, for more information regarding the treatment of plasma concentrations below the assay's lower limit of quantification (BQL).

Individual concentration-time profiles and median/mean profiles from each matrix will be plotted. Each of the figures will contain one plot on the untransformed scale (i.e. a linear plot) and one plot on the log transformed scale (i.e. semi-log plot). See Section 11.1.3 Pharmacokinetic Figures and Tables for details.

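### Tissue:plasma and fluid:plasma Cmax and AUC ratios compare profiles sampled on different schedules: a small effect for Cmax and partial AUCs, a large one for AUC(0-last), and time-matched is left undefined

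*Protocol*

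**What the plan says.** **Schedules.** Protocol Section 4.4 sets out the extra plasma sampling: "In addition to the paired blood plasma samples, blood plasma will be collected at additional timepoints through the extended safety visits". SAP Section 8.2 lists plasma at "Day 1 (pre-dose, 4hr), Day 3 (C48h), Day 5 (C96h), Day 8 (C168h), Weeks 4, 8, 12, 24, 36, and 52". For the female genital matrices it lists "Cervical tissue (CV) and cervicovaginal fluid (CVF) of CAB concentrations in women: Day 3 (C48h), Day 8 (Cd8), Weeks 4, 8, and 12", and RT and RF follow the same five times. Protocol Table 4 adds: "Vaginal tissue will be collected only on Day 3 (48h) and Week 8".

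**Ratios.** The protocol's secondary endpoints include "Tissue:blood plasma and fluid:blood plasma ratio of AUCs of intervals specified above" as well as concentration ratios at matched times. The Cmax ratio appears only in the SAP: the derivation table in Section 8 asks for tissue and fluid ratios to plasma, ending with "RF:blood plasma and RT:RF in men and women ratios for Cmax" and the AUCs. Tables 3.8 and 3.13 report Cmax and AUC ratios.

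**Derivation.** SAP Section 8.3 takes Cmax from the raw data of each matrix and AUC(0-last) up to the last quantifiable sample. Item 10 there, like Protocol Section 9.4.2, calls the AUC ratios time-matched. Neither says whether this means the same interval or the same sampling times. Item 10 does not mention Cmax. Section 8.3 derives no Cmax or AUC for VT, yet Section 8 and Table 3.8 list VT ratios of both.

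**The concern.** A ratio of two profile summaries describes distribution only if both are taken on the same footing. Here the plasma maximum is sought over seven post-dose samples to Week 12 (and three more after that), while the CT, CVF, RT or RF maximum is sought over five. One of the extra plasma samples, at 96 h, lies close to the expected peak. Plasma AUC(0-last) can also run 40 weeks beyond the last tissue sample. Part of any reported ratio would then come from the visit schedule. AUC ratios are a stated secondary endpoint, so a reader comparing compartments, or comparing the AUC(0-last) ratio with the AUC(0-Wk12) ratio, could take a schedule effect for a difference in penetration.

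**Working it through.** The plan gives no figure for this effect and no sizing to reproduce ("There was no formal calculation of power or sample size for this study"), so the check is a model calculation.

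**Inputs from the documents**
- Sampling times as above. Weeks 4, 8, 12, 24, 36 and 52 are 672, 1344, 2016, 4032, 6048 and 8736 h.
- Absorption rate KA: 9.19e-4/h in the updated population model and 4.54e-4/h in the previous one (Protocol 4.5).
- Half-life after injection: 21-50 days (Protocol 2.2). If absorption is rate-limiting, KA = ln 2/(50×24) = 5.78e-4 to ln 2/(21×24) = 1.37e-3/h.
- Oral peak 7.5 and trough 4.2 µg/mL (Protocol 4.5).

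**Assumptions**
- The oral peak-to-trough fall takes 22 h, so ke = ln(7.5/4.2)/22 = 0.0264/h. A lower value of 0.0173/h (half-life 40 h) is also used.
- Tissue is a constant fraction of plasma, so the correct ratio factor is 1.00.
- Between-subject variation in KA is about 50% CV. Errors are log-normal.

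**1. Direction.** The maximum over a set of samples is never below the maximum over a subset. The planned Cmax ratio is therefore at most equal to the shared-time ratio. This needs no model.

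**2. Typical subject.** C(t) = KA/(ke−KA) × (exp(−KA·t) − exp(−ke·t)), and tmax = ln(ke/KA)/(ke−KA). With KA 9.19e-4 and ke 0.0264, tmax = ln(28.73)/0.02548 = 132 h. Relative to the peak, C is 0.11 at 4 h, 0.79 at 48 h, 0.98 at 96 h and 0.99 at 168 h. The largest plasma sample is the shared one at 168 h, so the factor is 1.000. The 4 h sample is irrelevant. At KA 1.37e-3, tmax is 118 h, the 96 h sample (0.989) exceeds the 168 h sample (0.970), and the factor is 0.970/0.989 = 0.981.

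**3. Cmax with variation and noise** (simulation, geometric means)

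| Setting | Planned ratio ÷ shared-time ratio |
|---|---|
| KA 9.19e-4, no noise | 0.99-1.00 |
| KA 9.19e-4, 15% error in both | 0.93 (ke 0.0264) to 0.96 (ke 0.0173) |
| KA 4.54e-4, 15% error in both | 0.95 to 0.975 |

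Restricting plasma to the shared times returns 1.00 when the two errors are equal. With unequal errors (KA 9.19e-4, ke 0.0242, which is a 24 h fall), 30% tissue and 15% plasma error give 1.02 as planned and 1.085 on shared times. With 40% and 15% the values are 1.10 and 1.17.

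**4. Partial AUCs** (linear-up/log-down, no noise). At KA 9.19e-4 the factor is 0.986 for AUC(0-Wk4) and 0.992-0.993 for AUC(0-Wk12). Over half-lives of 21-50 days the ranges are 0.984-0.988 and 0.990-0.995.

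**5. AUC(0-last).** The share of total AUC beyond time T is ke/(ke−KA) × exp(−KA·T). At KA 9.19e-4 and T = 2016 h this is 1.036 × 0.157 = 0.162, so 0.838 of the total lies before Week 12. The share beyond Week 52 is negligible. Multiplying by the 0.992 from step 4 gives 0.83. If the last quantifiable plasma sample were Week 24, the share beyond it is 1.036 × 0.0246 = 0.0255, and the factor is 0.838/0.9745 × 0.992 = 0.85. With plasma to Week 52 the factor is 0.60 at KA 4.54e-4, 0.68 at 5.78e-4, 0.92 at 1.37e-3 and 0.97 at 2e-3 (the last KA is assumed and is not in the documents).

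**6. VT.** With samples only at 48 h and Week 8, the noise-free Cmax factor against full plasma is 0.63-0.82 over half-lives of 21-50 days.

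**The case against.** **A reader might infer that the Cmax ratio understates true penetration.** The documents do not support that. The downward direction is certain only against a shared-time ratio. Step 3 shows the sign against the true fraction reversing once tissue error is about 30% against 15% in plasma, and the documents give neither error. Matching also does not guarantee a truer value: with a noisier tissue maximum it leaves the upward part exposed. The protocol synopsis plans no geometric means for ratios, and on the arithmetic mean with equal 15-20% error (ke 0.0242) the planned value is about 0.95-0.96 and the shared-time value about 1.02-1.03. All of this stands.

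**A reader might infer a distortion of the comparison between men and women.** Absorption is slower in women (Protocol 4.5), but CT, CVF and VT exist only in women, RT and RF are optional for them, and the modelled sex comparison in SAP 8.4 uses plasma parameters only. Halving KA moves the Cmax gap by only about 1.5 percentage points at 15% error.

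**The AUC ratios are already called time-matched.** If that means the same sampling times, the AUC part disappears. But AUC(0-last) is defined to each matrix's own last quantifiable sample, and no text says plasma is cut back, so the gap is the missing definition.

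**The consequence is small.** The concentration ratios at matched times are unaffected, and the Cmax ratio is a descriptive output found only in the SAP. With 8 subjects and 15% error in each value, a ratio at one time has a standard error of about 0.15×√2/√8 = 7.5%, as large as the Cmax gap. This stands for Cmax and partial AUCs. It does not cover AUC(0-last).

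**Conclusion.** The point holds as a minor one about specification. The schedules differ, no rule restricts plasma to shared times, and time-matched is undefined. The Cmax effect relative to a shared-time ratio is negligible without noise and a few percent with it, nearly all of it from the assumed residual error and the 96 h sample. Partial AUCs are barely touched. The material case is AUC(0-last): if it is computed as its definition reads, the ratio at the updated KA is about 15-17% low, and by more with slower absorption. This depends on plasma staying quantifiable at least to Week 24; Protocol 4.6.1 expects residual drug for up to 52 weeks in some subjects. VT Cmax and AUC ratios from two samples are not interpretable. The sizes rest on a one-compartment model, a constant tissue fraction and assumed variation and error. The direction against a shared-time ratio rests on none of these. No statement about bias against the true fraction is justified.

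**What to change.** In SAP 8.3 item 10 and the notes to Tables 3.8 and 3.13:
- Define time-matched as the sampling times shared with the numerator matrix, with a common last time.
- For ratios only, recompute plasma Cmax, AUC(0-last) and the partial AUCs on those times. Name Cmax explicitly, since item 10 omits it. State which samples AUC(0-∞) uses; its effect is not sized here.
- Keep the full-profile plasma parameters for stand-alone reporting and for the sex comparison.
- Drop the VT Cmax and AUC ratios, or label them as not interpretable because they rest on two samples. Keep the VT concentration ratios at 48 h and Week 8.

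The cost is a second WinNonlin pass on a subset of plasma samples and a footnote, with no extra sampling. The downside is a ratio denominator that differs from the plasma parameter reported elsewhere, which the footnote should say. The footnote should also say that matching removes only the schedule effect, not any upward bias from a noisier tissue maximum.

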4.5. Dose Justification

Oral Dose:

Based upon the results through Week 48 of the Phase IIb, LAI116482 study, and in accordance with the pre-specified dose selection criteria at Week 24, CAB 30 mg PO once daily has been selected as part of short-term oral lead-in therapy in combination with rilpivirine for maintenance of virologic suppression in future clinical studies in subjects with HIV infection as well as for short-term oral lead-in therapy as CAB monotherapy prior to CAB LA injectable dosing in the ÉCLAIR and HPTN077 PrEP studies in healthy uninfected subjects [GlaxoSmithKline Document Number [2013N184048_01](#); DAIDS Document ID 11964, 2014]. Therefore, the CAB 30 mg oral dose will be administered during the oral lead-in phase of this study to assess safety and tolerability prior to the CAB IM injection.

LA Dose:

In an early study, a small cohort of healthy participants receiving two quarterly doses (Q12W) of CAB LA 800 mg IM achieved a geometric mean (CVb%) C_{τ} of 1.11 mg/mL (139%), approximately 6.7-fold above the PA-IC₉₀ and between the 5 mg and 10 mg oral doses. These data, as well other PK data following CAB LA following single or repeat doses ranging from 100 mg to 800 mg IM, were included in the initial population PK model. Based on the initial population PK model, CAB LA 800 mg IM given every 12 weeks (Q12W) was predicted to achieve a mean concentration above the 1.35 µg/mL target based on 10 mg daily oral dosing with the lower bound of the 90% confidence interval (CI) at ~4-fold PA IC₉₀. The overall range of predicted CAB C_{τ} values following CAB LA 800 mg IM was similar to that following once daily dosing of oral CAB 10 mg.

The Phase 2a 201120 (ÉCLAIR) study was undertaken to evaluate PK and safety following Q12W CAB LA 800 mg IM doses in healthy male participants. Evaluation of PK data from ÉCLAIR showed that 30 to 37% of CAB LA C_{τ} values were ≥4-fold PA-IC₉₀ following each of the three quarterly injections while 15 to 31% were below the PA-IC₉₀. Graphical evaluation of the CAB plasma concentration-time profiles suggests that absorption was more rapid among participants in the ÉCLAIR study than that observed in prior studies, resulting in higher peak and lower trough concentrations. Of note, the CAB LA nanosuspension formulation has remained essentially unchanged throughout the clinical development program, indicating that other factors are contributing to the observed PK differences. Given this information, a regimen of CAB LA 800 mg Q12W may not maintain sufficient exposures in all participants, particularly in males. The ongoing Phase 2a study 201103 (HPTN 077), which like ÉCLAIR is evaluating CAB LA 800 mg IM Q12W in healthy male and female participants, was amended to enroll a

second cohort with dosing of CAB LA 600 mg IM at two time points 4 weeks apart and every 8 weeks (Q8W) thereafter for 5 injection visits. A similar regimen (CAB LA 800 mg IM initial dose followed by 600 mg IM at two time points 4 weeks apart and Q8W thereafter) has been evaluated in HIV infected participants (n=115; 107 males and 8 females) in combination with rilpivirine (RPV) LA in study 200056 (LATTE-2). This regimen achieved a mean CAB C_{τ} of 1.53 $\mu\text{g/mL}$ (median 1.45 $\mu\text{g/mL}$) at Week 32, above the geometric mean C_{τ} value for the 10 mg oral dose in LATTE. At Week 32, the proportion of participants maintaining suppression of HIV in the Q8W arm was 95% as compared to 94% in the Q4W arm (CAB LA 800 mg IM initial dose followed by 400 mg IM every 4 weeks from Week 4, n=115).

The CAB population PK model has been updated with PK data from ÉCLAIR (an additional 94 males) and LATTE-2 (an additional 230 participants; 216 males and 14 females), significantly increasing the data in the population PK dataset. The absorption rate constant for the entire population following CAB LA for the new model was increased approximately 2-fold ($4.54 \times 10^{-4} \text{ hr}^{-1}$ to $9.19 \times 10^{-4} \text{ hr}^{-1}$; i.e., more rapid absorption) as compared to the previous model and resulted in higher peak to trough ratios than previously observed. Sex remains a significant covariate in the model affecting the absorption rate constant following LA administration (KA LA), reflecting slower absorption in females than in males. Additional data from HPTN077 will increase the data obtained from females in the model to improve understanding of the impact of sex on KA LA.

Simulations based on the updated population PK model have been conducted to evaluate several potential dosing regimens. Currently, the HPTN077 Cohort 2 regimen (CAB LA 600 mg IM at two time points 4 weeks apart and every 8 weeks (Q8W) thereafter) is planned for evaluation in long-term Phase 3 PrEP studies. CAB LA 600 mg IM is the largest CAB LA dose that can be administered by single injection (3mL of 200 mg/mL nanosuspension). For these reasons, a single 600 mg IM is the proposed dose for evaluation of plasma and tissue PK in this study. Simulated profiles following a single CAB LA 600 mg IM injection one week after discontinuation of the CAB 30 mg once daily oral lead-in to evaluate safety are shown for males and females separately (Figure 2, Figure 3). The profiles show the last oral dose, which are expected to achieve mean peak and trough concentrations of 7.5 $\mu\text{g/mL}$ and 4.2 $\mu\text{g/mL}$, respectively. Consistent with the impact of sex on absorption, males will achieve a higher C_{max} of ~3 $\mu\text{g/mL}$ than females, who will achieve a C_{max} of ~1.35 $\mu\text{g/mL}$. Plasma concentrations are expected to remain above 4x PA-IC₉₀ (0.664 $\mu\text{g/mL}$) for approximately 4 weeks and above PA-IC₉₀ (0.166 $\mu\text{g/mL}$) for approximately 8 weeks in 95% of males; greater variability in concentrations between 8 and 12 weeks post injection is expected in males. Plasma concentrations are expected to remain above the PA-IC₉₀ (0.166 $\mu\text{g/mL}$) in 95% of females throughout the 12-week tissue sampling period.

Figure 2 Predicted Median (90% PI) CAB Concentration-time Profile in Males following a single CAB LA 600 mg IM Injection (after a 1 week washout from 30 mg once daily oral lead-in)

[figure not shown]
[figure not shown]

Figure 3 Predicted Median (90% PI) CAB Concentration-time Profile in Females following a single CAB LA 600 mg IM Injection (after a 1 week washout from 30 mg once daily oral lead-in)

In a previous study, a modest correlation between plasma CAB concentrations and cervicovaginal and rectal tissue concentrations was observed following a single dose of CAB LA 400 mg IM in healthy male and female subjects (Section 2.1). As the proposed dose is 50% higher and tissue sampling will be conducted during the oral phase and following CAB LA administration, it is expected that tissue sampling will be conducted over an ~100-fold range of plasma concentrations (~0.05 μ g/mL to ~5 μ g/mL). The partitioning of CAB into genital tract and rectal tissue achieved over a 12-week window following a single CAB LA 600 mg IM dose will enhance our understanding of CAB LA as PrEP.

